## **E.5. DATA TRANSFORMATIONS**

### **E.5.1. Categorical Variables**

Many variables in the SECOND Trial Resident Survey and Program Directors' Survey are categorical. Several are measured using 5-point Likert-type scales. Frequencies of all variables in their untransformed state will be tabulated and examined. However, categorical variables may be recoded for reasons that may include:

- Re-coding and collapsing categories to avoid small cells, which we define in this study as having  $\leq 5$  observations
- Dichotomizing to facilitate analyses – in particular, the interpretability of associations

### **E.5.2. Continuous Variables**

The distribution of natural and derived continuous variables (for example, program-level rates of resident respondents) in the main analyses will be characterized by its mean, standard deviation, median, skewness, and kurtosis, among other statistics. Continuous variables may be transformed for reasons that may include:

- Discretization due to non-normality or to facilitate interpretation of associations
- Log-transformation or other transformation to address non-normality, particularly in the context of conforming to statistical assumptions underlying a particular modeling technique

## **E.6. PROCEDURES FOR MISSING DATA**

### **E.6.1. Complete Case Analysis**

Primary analyses will rely on complete case analysis in which only observations for which complete data on all variables for a given model exist. The drawback of this approach is that if data are not missing *at random*, parameter estimates may be biased. A second limitation of this approach is that, depending on the volume of incomplete data, analytic sample attrition due to missing data may attenuate statistical power. However, because the SECOND Trial Resident Survey is optional to residents, and because many survey items may be socially sensitive, missing data are likely to be missing *not at random*. Although patterns of missing data will be explored and multiple imputation methods for addressing missingness will also be explored, complete case analysis will be the first approach due to its simplicity. Limitations of this approach will be disclosed in reports of analyses relying on complete case analyses.

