## **D.8. SAMPLE SIZE/POWER CALCULATIONS**

### **D.8.1. Data for Sample Size/Power Calculations**

Data for power calculations came from the 2019 ABSITE Survey and are based on data from residents who were clinically active. Calculations were made for the primary endpoint only, burnout (§C.1 and §E.1).

In the 2019 ABSITE survey data, complete data on burnout survey items Q15A-Q15F and burnout scores were available for 5,962 clinically active residents from 300 programs. Clinically inactive residents were excluded, as were residents that had incomplete data on burnout survey items Q15A-Q15F. Program sizes, measured in terms of the number of respondents, ranged from 3 to 54, with a mean of 19.873 (SD=9.647).

Because we intend to randomize programs within strata defined on the basis of program-level mean burnout using prior data, we also used data from the 2018 ABSITE survey in order to define program-level strata for our preliminary models from which parameters were obtained for power calculations.

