### **D.8.3. Preliminary Models**

Using ABSITE data from 2018, we computed IRT-derived T-scores for residents (2018 ABSITE survey items Q11A-Q11F). We then computed program-level mean burnout T-scores, and then stratified programs into quartiles based on these program-level mean burnout scores. These 2018 burnout quartiles were merged back to the 2019 ABSITE data. Programs that were missing in the 2018 ABSITE were grouped into a fifth stratum.

We estimated (a) a two-level (“empty”) hierarchical linear model with random program intercepts; (b) an “unadjusted” hierarchical model adjusting only for program strata (quartile of 2018 burnout scores); and (c) an “adjusted” model that controlled for resident gender (female (reference male)); post-graduate year (PGY); resident relationship status; resident race (nonwhite (reference white)) and program quartile of burnout based on program-level mean burnout scores from 2018, program geographic region (Southeast, Midwest, Southwest, West (reference Northeast)); program type (community, military (reference academic)), and program size.

The intraclass correlation from the empty model was 0.082, suggesting that roughly 8% of total variance in resident burnout scores in 2019 were attributable to the program level. Controlling for program quartile of 2018 mean burnout scores in the “unadjusted” model reduced the program-level (Level-2) variance component by 75%, from 7.413 to 1.821, and reduced the ICC to 0.021. Including additional resident and program covariates reduced the Level-2 variance component by 86% compared to

the empty model. The ICC in the adjusted model was 0.012 – i.e., approximately 1% of the variance in resident burnout scores was attributable to the program level after controlling for a program’s prior year mean burnout T-score and resident/program characteristics.

The population-averaged mean burnout score estimated from the empty model was 49.753 (SD=9.137, square root Level 1 residual variance). The mean resident burnout score from the “unadjusted model” with controls for 2018 program mean burnout was 46.970 (SD=9.150). The mean resident burnout score from the adjusted model was 45.933 (SD=9.027, Level 1 residual).

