Using the constant estimated from the adjusted model as an estimate of the mean burnout score in Control (45.933) and the standard deviation of the Level-1 error component as the estimate of the standard deviation (9.027) around mean burnout scores in Control and assuming  $\alpha_{final}=0.0443$  for the final analysis, 80% power and  $ICC=0.012$ , we computed minimal detectable differences for a variety of hypothetical sample sizes, as reported in EXHIBIT D.8-B.

The scenario yielding the smallest detectable difference in adjusted mean burnout scores would be one in which there are 300 programs total, 150 programs in each arm with a mean of 25 residents per program. In this scenario, given our assumptions, we expect to be powered at 80% to detect a relative difference in mean burnout scores of -1.46%.

In a conservative scenario with 100 programs randomized to each study arm (200 programs total) and an average of 15 residents per program, we expect to be powered at 80% to detect a relative difference in mean burnout scores of -2.22%.

In a moderate scenario with 110 programs randomized to each study arm (220 programs total) and an average of 20 residents per program, we expect to be powered at 80% to detect a relative difference in mean burnout scores of -1.87%.

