#### ***E.1.2.2. IRT GRM Analysis of Burnout Using 2019 ABSITE Data***

We used data from the 2019 ABSITE Survey to perform an IRT GRM analysis of the 6 burnout items in the 2019 ABSITE data in order to develop our outcome measure.

In this work, 2019 ABSITE residents who did not report being in a clinically active year (Item Q1==1) were excluded. This work was performed on complete cases. Therefore, residents with any missing data on items Q15A-Q15F were also excluded. (Preliminary work retained residents who were clinically inactive, as well as residents with some missing data. Results were similar.)

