#### E.4. OTHER MEASURES

Other measures that may be used in statistical analyses may include, but are not limited to:

Resident Characteristic	SOURCE	Item Name	Variable Name	Measure Type/Values
PGY level	ABS	level	pgy	Ordered Categorical PGY1, PGY2, PGY3, PGY4, PGY5
Gender	ABS	Gender	gender	Unordered Categorical Male, Female
Clinically active	ABS	Q1	clinactive	Unordered Categorical Yes, No, Unsure
Relationship status	ABS	Q2	marital	Unordered Categorical Married, Not Married but in a Relationship, Not Married and Not in a Relationship, Divorced/Separated, Widowed
Number of children	ABS	Q3	children	Ordered Categorical 1, 2, 3, 4, 5+
Pregnant/Adopting/Expecting	ABS	Q4	children2	Unordered Categorical Yes, No, Unsure
Race	ABS	Q5a-Q5g	nativeamerican, asian, black, pacific, white, raceother, raceprefer	Dichotomous: American Indian/Alaska Native Asian Black/African American Native Hawaiian/Other Pacific Islander White Other

				Prefer Not to Say
Ethnicity	ABS	Q6	hispanic	Unordered Categorical Hispanic or Latino, Not Hispanic or Latino, Prefer Not to Say
LGBTQ	ABS	Q7a-7g	straight, gay, bisexual, orientother, trans, otherident, identprefer	Dichotomous: Straight Gay/Lesbian Bisexual Other Orientation Transgender Other Gender Prefer Not to Say

Program Characteristic	SOURCE	Item Name	Variable Name	Measure Type/Values
Proportion Residency Program International Medical Graduates (IMG)	ABS	propimg	PCTIMG	Continuous Numeric
Proportion Residency Program Male	ABS	propmale	PCTMALE	Continuous Numeric
Program Size	ABS	progsize	PGMSIZE	Continuous Numeric
Program Type	ABS	progtype	PGMTYPE	Categorical Academic, Community-Based, Military
Geographic Region	ABS	Geo	Geo	Categorical Northeast, South, Midwest, Southwest, West
Current Number of PGY 5 Residents	ABS	PGY5_N	PGY5_N	Continuous Numeric
Number of ABSITE Examinees	ABS	RES_N	RES_N	Continuous Numeric
Proportion Faculty Female	AAMC	percfemalefac	pctfemfac	Continuous Numeric

Chair Gender		chair_gender	ch_gender	Unordered Categorical: Male, Female
Program Director Gender		pd_gender	pd_gender	Unordered Categorical: Male, Female

Patient Characteristic	SOURCE	Item Name	Variable Name	Measure Type/Values
Treatment Group	SECOND	tx_arm	TREAT	Dichotomous Categorical Intervention, Control
Age	NSQIP	age	age	Continuous Numeric
Age Group	NSQIP	agegroup	AGECAT	Ordered Categorical <65, 65-74, 75-84, 85+
ASA Class	NSQIP	asaclas_c	ASACLASS45	Categorical Class 1, Class 2, Class 3, Classes 4&5

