#### F.3.1.2. Adjusted Analyses

Covariate adjustment in evaluations of randomized trials is generally done for purposes of increasing statistical efficiency by reducing variance within treatment groups. Covariate adjustment is also sometimes also undertaken on the basis of chance imbalance of baseline characteristics between study groups. Although programs will be randomized to treatment arms in this study, we anticipate considerable variation in the number of ABSITE respondents per program. In the 2019 ABSITE data, the average program had 23 resident respondents (mean=23.11, SD=11.15; coefficient of variation=48%), but the range spanned from a minimum of 3 residents per program to a maximum of 59 residents per program. Such dispersion in cluster sizes may lead to imbalance of resident characteristics

Thus, our analytic approach to evaluating our primary hypothesis will be to estimate a 2-level hierarchical linear model of the general form:

$$y_{ij} = \alpha_0 + \beta_0 TREAT_j + \beta_1 x_{1ij} + \beta_2 x_{2ij} + \cdots + \beta_k x_{kij} + \gamma_1 z_{1j} + \cdots + \gamma_m z_{mj} + \zeta_j + \epsilon_{ij}$$

where  $y_{ij}$  is the burnout T-score of resident  $i$  in program  $j$ ,  $TREAT_j$  is the study arm assignment of program  $j$ , and  $x_{1ij}$ - $x_{kij}$  are resident-level covariates and  $z_{1j}$ - $z_{mj}$  are program-level covariates to be adjusted for, including sampling stratification variables. In this model, under randomization of programs to study arms, the coefficient  $\beta_0$  is the adjusted population-averaged intent-to-treat estimate of the effect of assignment to intervention on mean resident burnout. A coefficient  $\beta_0 < 0$  that is statistically

significant with a one-tailed  $p<0.0443$  provides evidence supporting the effectiveness of the intervention over usual care. Other parameters in the model are the constant ( $\alpha_0$ ), coefficients on other resident-level covariates ( $\beta_1-\beta_k$ ), coefficients on program-level covariates ( $\gamma_1-\gamma_m$ ), program-level random intercepts ( $\zeta_j$ ) and individual-level errors ( $\epsilon_{ij}$ ).

Covariates may include variables listed in §E.3.: resident gender; resident relationship status; resident race; program type; program size; and randomization variables such as the quartile of program  $j$  ranked by 2019 program-level mean burnout scores. This list of covariates is subject to change.

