Covariates will not include any other resident-level outcome or behavioral variable(s) that may be affected by the intervention as doing so may introduce endogeneity. Thus, for example, measures of career satisfaction, duty hour adherence, mistreatment, discrimination/harassment etc. will not be considered as controls in the evaluation of burnout.

Any structural measures – i.e., measures of program characteristics, policy, and/or programs related to burnout will not be controlled for in the primary analysis as doing so might over-control and attenuate the intent-to-treat estimate of the treatment assignment effect.

We will examine the mean, median, skewness and kurtosis values of the dependent variable to assess the normality of the dependent variable. If there is evidence of non-normality in the dependent variable, we may consider an appropriate transformation of the dependent variable; however, generalized linear mixed models are flexible and can accommodate alternative distributional assumptions regarding  $y_{ij}$  without altering the original scale of  $y_{ij}$ .

In accordance with the decision of the Principal Investigators, estimates from the adjusted analyses of the primary outcome will be reported as the primary findings of this study, although both adjusted and unadjusted analyses will be conducted.

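### The primary adjusted model is complete-case on every covariate, so scored residents leave the headline estimate when a baseline covariate is missing

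*SAP*

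**What the plan says.** Section E.6.1: "Primary analyses will rely on complete case analysis in which only observations for which complete data on all variables for a given model exist". The same section says missing data are probably not missing at random, gives simplicity as the reason for the method, and promises to disclose the limitation. Section E.6.2 makes multiple imputation depend on inspecting the data.

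Section F.3.1.2 decides which model carries the result: "estimates from the adjusted analyses of the primary outcome will be reported as the primary findings of this study". Its candidate covariates are "resident gender; resident relationship status; resident race; program type; program size", plus the randomisation stratum, and the list may still change.

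Section F.1.1 commits the main analysis to including every program and resident as assigned.

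For scoring and power, the population was defined by clinical activity and outcome alone. Section D.8.1: "Clinically inactive residents were excluded, as were residents that had incomplete data on burnout survey items Q15A-Q15F". Section E.1.2.2 likewise excludes "2019 ABSITE residents who did not report being in a clinically active year". Neither mentions covariates.

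Section E.4 stores race as "nativeamerican, asian, black, pacific, white, raceother, raceprefer", the last being a decline-to-answer option. The plan does not say whether that answer counts as missing.

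**The concern.** Read together, E.6.1 and F.3.1.2 let a blank baseline item remove a resident whose outcome was measured and whose program was randomised. A program with no recorded type or size would leave entirely. The set of people behind the headline estimate then depends on which covariates are finally chosen, and that choice is open.

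The covariates are in the model to gain precision. A missing covariate value is no reason to discard an observed outcome, and doing so departs from F.1.1. At stake are some precision, how well the analysed residents represent those randomised, and possibly one of the five randomisation strata. Exhibit D.8.A shows a loss of this kind in the plan's own data: the sample shrinks only when covariates enter.

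**Working it through.** **1. Loss in the planning data (Exhibit D.8.A).** All 5,962 residents had complete burnout items (D.8.1), so no one was lost for a missing outcome.
- Residents, strata-only to adjusted model: 5,962 − 5,075 = 887; 887/5,962 = 14.9%.
- Programs: 300 − 237 = 63; 63/300 = 21.0%.
- The lost programs held at most 887 residents, a mean of at most 887/63 = 14.1. The retained programs averaged at least 5,075/237 = 21.4.

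**2. How much of this is stratum 5?** The exhibit's footnote says stratum 5 (programs without 2018 data) fell out of the adjusted model. The confidence intervals of the strata-only model allow a rough reconstruction. It treats program sizes as equal within the quartile group and within stratum 5, with variance components 1.821 and 83.721.
- Variance of the constant (stratum 1 mean): ((47.615 − 46.325)/3.92)² = 0.108.
- Variance of the stratum 5 contrast: ((1.430 + 0.885)/3.92)² = 0.349. The stratum 5 mean therefore has variance 0.349 − 0.108 = 0.240, or information 1/0.240 = 4.16.
- By the same subtraction, strata 2 to 4 have variances 0.087, 0.087 and 0.090. Total information for strata 1 to 4 is 43.2.
- Information = K/(1.821 + 83.721/m) for K programs of size m. If stratum 5 is all 63 lost programs, 63/4.16 = 15.15, so m = 83.721/(15.15 − 1.821) = 6.3, or about 396 residents. The other 237 programs then have m of about 22.8, about 5,413 residents. The total is 5,809 against the actual 5,962.
- Matching 5,962 exactly gives about 224 quartile programs and 76 in stratum 5, with about 387 residents.

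So stratum 5 plausibly accounts for most or all of the lost programs and 387 to 396 residents. The remaining loss is 887 − 396 = 491 of 5,566 (8.8%) to 887 − 387 = 500 of 5,575 (9.0%).

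**3. Reproduce the plan's power figures.** SE = 9.027 × √[(1 + (m − 1) × 0.012)/m × (1/k₁ + 1/k₂)]. Detectable difference = (2.011 + 0.842) × SE, at two-sided 0.0443 and 80% power. For 110 per arm and m = 20, SE is 0.3016 and the difference 0.86. For 100 per arm and m = 15, SE is 0.3562 and the difference 1.02. Both match Exhibit D.8.B.

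**4. Apply it to the trial.** Programs: 106 and 103 (Exhibit D.9). Mean cluster size is assumed to be the planning value, 19.87. The one-tailed column replaces 2.011 with 1.703, because F.3.1.2 states a one-tailed test.

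| Scenario | SE | Two-sided | One-tailed |
|---|---|---|---|
| No loss | 0.3103 | 0.885 | 0.789 |
| 5% of residents lost | 0.3168 | 0.904 | 0.806 |
| 10% of residents lost | 0.3239 | 0.924 | 0.824 |
| 14.9% of residents lost | 0.3314 | 0.945 | 0.843 |
| Three programs lost (104 and 102) | 0.3125 | 0.892 | 0.795 |
| Full planning loss repeated | 0.3388 | 0.967 | 0.862 |

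The three-program row reflects Exhibit D.9, where the types sum to 107 + 94 + 5 = 206 of 209. Two-sided power at 0.885 falls from 80% to 74.5% with 14.9% of residents lost, and to 72.6% if the full planning loss recurs. With larger clusters the differences are smaller: no loss and 14.9% loss give 0.834 and 0.889 at m = 23.11 (the F.3.1.2 mean), and 0.722 and 0.765 at m = 34 (about the Exhibit D.9 mean, which may include residents not clinically active).

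**The case against.** The strongest reply is that the planning loss says little about the trial. It came from a national file, its stratum 5 was defined on 2018 data, and its model used region and PGY level, which the F.3.1.2 list does not name. Much of the loss looks like one group of small programs and not general covariate non-response. This stands, and it is why 14.9% and 21.0% are not used as forecasts.

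Whole-program loss in the trial is also speculative. Size and type are ABS fields, Exhibit D.9 already reports size and gives type for 206 of 209 programs, and the other three may be a gap in the table. This stands too.

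The plan has partial safeguards. E.6.1 discloses the limitation, and both the unadjusted model (F.3.1.1) and the program-level model (F.3.1.3) can keep every scored resident. These help a reader judge robustness, but none is the headline result, and disclosure does not restore excluded residents.

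A reader might infer that the complete-case rule biases the treatment effect, or leaves the trial underpowered. The documents support neither. Nothing shows that covariate missingness differs by arm, and every scenario above stays below the 1.02 that the plan accepted for its case introduced with "In a conservative scenario with 100 programs randomized to each study arm".

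**Conclusion.** The point holds as a should-fix matter of modest size. The plan states a rule that discards measured outcomes for missing baseline covariates in the analysis it reports as primary, against its own intent-to-treat statement. If 10% to 15% of residents were lost, the two-sided detectable difference would rise from about 0.885 to 0.92–0.95, less in absolute terms if clusters are larger. Losing a randomisation stratum, as happened to stratum 5 in the planning model, is possible but not established for the trial.

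These figures assume 19.87 residents per program and unchanged SD and ICC. Covariate missingness among enrolled residents is not given, so 5% to 14.9% is an assumed range. The stratum 5 attribution is an approximation from published intervals: the document says only that the term dropped out through collinearity, and does not say which variable caused the sample to shrink.

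**What to change.** Revise E.6.1 and F.3.1.2 as follows.
- Define the primary analysis set as all clinically active residents with a burnout T-score in randomised programs, matching the exclusions already used for scoring and power.
- Complete program type and size from the enrolment forms and the ACGME descriptive data agreed in D.5.4, so that no program drops out and all five strata, including stratum 5, stay in the model.
- Code missing or decline-to-answer resident covariates as a separate category, fixed before analysis.
- Report the complete-case adjusted model as a sensitivity analysis.

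The cost is a few lines of SAP text and a little code. Covariate coefficients become less interpretable, but they are not of interest here.

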### **E.6.2. Multiple Imputation**

Data from the SECOND Trial Resident Survey will be inspected and patterns of missing data will be explored and characterized to ascertain whether or not data may be missing at random. If the data suggest it would be reasonable to do so, multiple imputation by chained equations (MICE) will be used to fill missing values.

## **SECTION F**

### **STATISTICAL METHODS AND PLANNED ANALYSES**

---

## **F.1. ANALYSIS PRINCIPLES**

### **F.1.1. Intent-to-Treat**

An intent-to-treat (ITT) approach will be adopted for the main analysis. In this approach, all programs and residents will be included in the analysis “as assigned,” irrespective of whether programs adopted (Intervention Arm) or did not adopt (Control) any organizational changes or measures during the study period to address resident wellbeing and/or the learning environment. The ITT estimate of the intervention effect will be biased if exposure is independent of (un)observable characteristics/features of programs and residents that would be correlated with both exposure and outcomes (i.e. programs and residents are randomized to exposure); if attrition and missing data are at random and if endpoints are measured without bias.

The ITT approach is particularly appropriate for this particular study due to the nature of the intervention. The intervention is the provision (or ‘offer’) of information: (a) program-specific feedback on resident wellness outcomes, as well as on the learning environment; and (b) a multicomponent Wellness Toolkit of various strategies for program-level organizational responses to promote and/or improve resident wellness and the learning environment within a program. The intervention was designed as an “offer of information” because the Principal Investigators believe different programs have different problem areas – i.e. areas that need improvement with respect to resident wellness and the learning environment. Thus, rational improvement should be targeted to program-specific problem areas. Therefore, programs may (or may not) adopt different measures to address different problems.

